## **STATISTICAL ANALYSIS PLAN**

For each of the three arms of the study we plan to recruit a minimum of 35 subjects. The total number of subjects is consistent with both our initial behavioral results in a group of 35 patients and seminal neuroimaging papers that suggest numbers of at least 20 subjects per group are necessary for adequate reliability of fMRI results (Murphy and Garavan, 2004; Thirion et al., 2007) – assuming certain standard estimates of signal-to-noise, spatial smoothing, and BOLD time series duration that are well-established in the fMRI literature across studies including perceptual, attentional, language-related, and executive tasks. Based on our previous data, for a behavioral effect size of 0.5 at a significance level of  $p = 0.05$ , our sample size will provide at least 88% power to detect a behavioral difference in a 2x2 ANOVA with factors of group and drug. For neuroimaging, our sample size will provide at least 80% power to detect a difference in the BOLD signal of 0.5% in a 2x2 (group x drug) ANOVA at a two-tailed significance of  $p = 0.05$ , corrected (Desmond and Glover, 2002). For PET imaging, our sample will provide at least 80% power to detect correlation of 0.3, which is on the lower end of effects observed in related studies at a two-tailed significance of  $p = 0.05$  (Berry et al., 2017; Jonasson et al. 2017; Kodaka et al. 2013).

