We will administer an extensive questionnaire listing contraindications to MRI scanning. Because the MRI scanner attracts certain metals, subjects who may have metallic objects in their bodies will be excluded. (As an additional measure of protection, we will use a hand-held metal detector to screen subjects before entering the scanner.)

Subjects will provide a saliva sample in order to determine catechol-O-methyltransferase (COMT) and dopamine receptor subtype 2 (DRD2) genotypes. DNA extraction and analysis will be conducted using standard methods to assess the Val158Met polymorphism of the COMT gene and the A1+ polymorphism in the DRD2 gene. Examiners and researchers who interact with study subjects or study data will remain blinded to genotype until the end of the study. Furthermore, genes affecting dopamine metabolism in addition to COMT and DRD2 will be examined (including the dopamine transporter variable number tandem repeat (DAT VNTR) and dopamine receptor subtype 4 single nucleotide polymorphism 521 (DRD4 SNP-521)). In order to further assess potential contraindications to tolcapone, a blood sample will be tested for routine chemistries including white cell count, red cell count, platelet count, hemoglobin, hematocrit, mean cell volume (MCV), mean cell hemoglobin (MCH), mean cell hemoglobin concentration (MCHC), red cell distribution width (RDW), mean platelet volume (MPV), neutrophils, lymphocytes, monocytes, eosinophils, and basophils. Additionally, because of potential hepatic effects of tolcapone, a hepatic screen will assay total protein, albumin, globulin, A/G ratio, bilirubin (total, direct, and indirect), alkaline phosphatase, aspartate aminotransferase

(AST, aka serum glutamic oxaloacetic transaminase (SGOT)), and alanine aminotransferase (ALT, aka serum glutamic pyruvic transaminase (SGPT)). Elevation of plasma bilirubin, AST (SGOT), ALT (SGPT), or alkaline phosphatase greater than 3 times normal values will be grounds for subject exclusion. (Note that ongoing monitoring of liver enzymes will not be necessary, as only a single, counterbalanced dose of tolcapone will be administered to each subject.) The blood sample may also be used for genetic testing if the saliva sample is non-diagnostic, compromised, or otherwise unavailable. Tests for blood chemistries following phlebotomy are currently performed at Quest Diagnostics in Berkeley, CA or the main laboratory at UCSF.

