Subjects will then be urine-screened for illicit drug use (Biotechnostix) and screened for intoxication via breathalyzer (Lifeloc Technologies). To confirm that subjects do not have potential drugs of abuse in their system, an on-site rapid urine-screening and a breathalyzer test will be done before administering tolcapone or placebo. Urine-screening will be done via an integrated test cup that includes a temperature sensor. The drug classes detected include cocaine, amphetamine, methamphetamine, tetrahydrocannabinol (THC), and opiates. Additionally, two opiates (methadone and oxycodone) may not be reliably detected by the 5-Test Integrated cup, so urine dipstick screening (Innovacor, Inc.) will also be performed on each subject's urine sample for these two

compounds. These drugs have been chosen due to their possible interaction with tolcapone and their possible cognitive and cardiovascular effects. No identifiers will be put on the test cup and it will be read immediately and discarded by the researcher. Similarly, the results of the breathalyzer will be read and then the test will be discarded. Moreover, due to the potentially sensitive nature of this information, the results will not be written down. Subjects who test positive for any of these substances will be excluded from further participation in the study. Subjects will also be excluded if they regularly use medications that affect dopamine levels, or will have used these medications within two weeks of tolcapone administration (including tolcapone, except as part of our study, or any of the following: levodopa/carbidopa, entacapone, amantadine, pergolide, pramipexole, ropinirole, selegiline, isocarboxazid, phenelzine, tranylcypromine, clozapine, olanzapine, quetiapine, risperidone, ziprasidone, aripiprazole, fluphenazine, haloperidol, perphenazine, pimozide, thiothixene, trifluoperazine, loxapine, molindone, chlorpromazine, mesoridazine, thioridazine, dextroamphetamine, dexmethylphenidate, or methylphenidate).

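### Does the single 88% power figure for the behavioural 2x2 ANOVA need to be restated because it names neither the effect nor the metric?

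*Combined protocol and SAP*

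**What the plan says.** The section headed Statistical Analysis Plan sets recruitment first: "For each of the three arms of the study we plan to recruit a minimum of 35 subjects". It then gives the behavioural power: "Based on our previous data, for a behavioral effect size of 0.5 at a significance level of" 0.05, "our sample size will provide at least 88% power to detect a behavioral difference in a 2x2 ANOVA with factors of group and drug". The neuroimaging sentence that follows uses the same factors, "in a 2x2 (group x drug) ANOVA at a two-tailed significance of" 0.05, corrected.

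The Study Protocol section indicates that drug is a within-subject factor. Screening is done "before administering tolcapone or placebo", and "only a single, counterbalanced dose of tolcapone will be administered to each subject", which describes a crossover against placebo.

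The power sentence leaves out five things: which ANOVA effect is meant, the metric of the 0.5, the correlation between sessions, the sidedness of the behavioural test (the BOLD and PET sentences do state theirs), and which of the three arms form the two groups.

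**The concern.** In a mixed 2x2 design the group effect is tested on subject means. The drug effect and the interaction are tested on tolcapone-minus-placebo change scores. A higher correlation between sessions shrinks the variance of the change scores and inflates that of the subject means, so it raises interaction power and lowers group power. One power figure for the whole ANOVA therefore has no definite meaning until the effect is named.

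The stake would be interpretation. If the aim is to show that tolcapone acts differently in two groups, a reader may take a null interaction as coming from a test with 88% power when the true figure is much lower. With no effect named, any of the three could later be presented as the one the study was sized for.

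**Working it through.** **Inputs.** From the Statistical Analysis Plan: at least 35 subjects per arm, three arms (3 × 35 = 105), effect size 0.5, level 0.05, power at least 88%. Assumed, because the documents do not say: two-sided tests, two groups of 35 (70 in all) unless stated otherwise, and between-session correlation ρ, varied over 0, 0.5 and 0.8. Power is from the noncentral t distribution with noncentrality δ.

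**Reproducing 88%.** With 0.5 as a raw-SD difference, the drug main effect over 70 subjects has δ = 0.5·√70/√(2(1−ρ)). At ρ = 0, δ = 2.96 and power is 83%. At ρ = 0.5, δ = 4.18 and power is 98.5%. It equals 88% at ρ of about 0.13. A one-sided paired test in a single arm of 35 at ρ = 0.5 gives 89.5%, but that is not a 2x2 test. So 88% can be reached, but not from one identifiable set of inputs.

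**The readings that fail.** Two groups of 35, 68 degrees of freedom, 35/2 = 17.5:

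- Interaction as a 0.5 SD between-group difference in drug effect: δ = 0.5·√17.5/√(2(1−ρ)).
- Group: δ = 0.5·√17.5/√((1+ρ)/2).

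| ρ | Interaction δ | Interaction power | Group δ | Group power |
|---|---|---|---|---|
| 0 | 1.48 | 31% | 2.96 | 83% |
| 0.5 | 2.09 | 54% | 2.42 | 66% |
| 0.8 | 3.31 | 90% | 2.20 | 58% |

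The interaction reaches 88% only from ρ of about 0.78, and the group effect only at ρ of about −0.13 or below. If all 105 subjects are split 52 v 53, the thresholds are 0.67 or more and 0.31 or less, so no single ρ serves both effects on this reading.

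**The readings that hold.** If 0.5 is Cohen's f, the noncentrality of the F test is f²·N·2/(1−ρ) for drug and interaction, and f²·N·2/(1+ρ) for group. With N = 70 the smallest value over the three correlations is for group at ρ = 0.8: 0.25 × 70 × 2/1.8 = 19.4, with power 99%. Every other case is higher.

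If 0.5 SD is converted to f = 0.25, the interaction is a half-contrast, equal to a 1.0 SD between-group difference in drug effect. With all 105 subjects in two groups and ρ = 0, the noncentrality is 0.0625 × 105 × 2 = 13.1 for each effect and power is 94.8%. In the near-even split all three effects stay at 88% or more for ρ between −0.31 and 0.31.

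**What this shows.** The same printed 0.5 and 0.05 give anything from 31% to over 99%, depending on inputs the sentence does not state. That is enough to call it incomplete, and not enough to call it wrong.

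**The case for a change.** The strongest case for a change is that the interaction is the natural target of a group-by-drug design. With 35 v 35, ρ = 0.5 and a 0.5 SD between-group difference in drug effect, it has 54% power. A rewording would cost nothing in recruitment and would tell readers what a null interaction is worth. It could be put in change-score SD units, which need no correlation: 35 v 35 gives 88% power for 0.76 SD.

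Part of this stands. The omissions are real, and if the interaction on that scale was intended, 88% would be overstated unless ρ is about 0.78 or more. But the premise is not in the plan. It refers to one behavioural difference. It does not name the interaction, and it does not claim 88% for group and interaction jointly, so showing that both cannot be had at once answers a claim nobody made. The rewording would also have to declare the interaction confirmatory and rank the other effects below it, and the plan contains no such ranking. Its figures would rest on a guess about which arms form the two groups. Genotyping is planned, so the groups could even lie within one arm, where those detectable differences would not apply.

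**Conclusion.** No change to the plan follows. The power sentence is under-documented, and that is the whole of the point. The figure of at least 88% holds for the drug main effect over 70 subjects once ρ is about 0.13 or more, and for all three effects with 70 subjects at the correlations examined if 0.5 is Cohen's f. It fails for a 0.5 SD between-group difference in drug effect with 35 v 35 unless ρ is about 0.78 or more. The documents do not say which of these was meant, and the 0.5 is attributed to earlier data that they do not show.

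The sentence justifies a sample size and sets no test, estimand or decision rule. If the study runs as planned, its completion would alter no result. A reader judging a null interaction should rely on the confidence interval for the difference in drug effect, which shows what the data exclude whatever the planned power. An analyst can add the missing inputs when reporting; which effect is primary remains the investigators' decision.

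This conclusion rests on drug being within-subject, two-sided testing, two groups of 35 where so stated, and no loss of subjects. Dropout below the recruited minimum would lower every figure above.

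### Does the PET power claim (at least 80% for a correlation of 0.3) fail because the SAP does not say which subjects it covers?

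*Combined protocol and SAP*

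**What the plan says.** All the relevant text is in the one paragraph of the Statistical Analysis Plan.

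- Recruitment: "For each of the three arms of the study we plan to recruit a minimum of 35 subjects". The total of 3 × 35 = 105 is not printed but follows directly.
- Basis for the size: "The total number of subjects is consistent with both our initial behavioral results in a group of 35 patients". The same sentence also cites imaging literature supporting at least 20 per group.
- Behavioural and fMRI power: both are framed as a two-by-two analysis of group and drug; the fMRI target is a "difference in the BOLD signal of 0.5% in a 2x2 (group x drug) ANOVA".
- PET power: "For PET imaging, our sample will provide at least 80% power to detect correlation of 0.3", two-sided at 0.05. The plan places this value toward the low end of those seen in related work.

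The PET sentence names no arm, no subset, no number of scans, no pair of variables and no allowance for unusable data. PET procedures are not described elsewhere in the available text.

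**The concern.** Power for a correlation depends almost entirely on the number of pairs, and the PET sentence does not give that number. The only sample figure in the paragraph is the per-arm minimum. A reader who carries 35 into the PET sentence finds a claim of at least 80% where the true figure is near 42%. A reader who takes the two groups of the preceding analyses and uses 70 finds about 72%. On either reading the claim is too generous.

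The stakes would be real if one of those tests were the intended one. With 35 subjects, the 95% confidence interval around an observed correlation of 0.3 runs from -0.04 to 0.58, so a non-significant result would say little about whether a correlation of that size exists. An undefined population could also let the choice between within-arm and pooled testing be made after the data are seen. A pooled correlation with no term for arm can in addition pick up differences in arm means on both measures.

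**Working it through.** **Inputs from the Statistical Analysis Plan:** r = 0.3; two-sided alpha 0.05; target power at least 80%; three arms; at least 35 recruited per arm.

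**Input not given:** the number of subjects with usable PET data. The totals 35, 70 and 105 are therefore tried in turn.

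**Formula (Fisher z):** power = Φ( atanh(r) × √(n − 3) − 1.960 ), with atanh(0.3) = 0.3095.

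**The plan's own figure first, n = 105:** 0.3095 × √102 = 3.126; 3.126 − 1.960 = 1.166; Φ(1.166) = 87.8%. The exact distribution of r gives 88.1%. The stated lower bound of 80% is met.

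**The other two readings:**

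| Subjects | atanh(0.3) × √(n − 3) | Minus 1.960 | Power (Fisher z) | Power (exact) | Smallest r with 80% power |
|---|---|---|---|---|---|
| 35 (one arm) | 1.751 | −0.209 | 41.7% | 42.5% | 0.46 |
| 70 (two arms) | 2.534 | 0.574 | 71.7% | 72.3% | 0.33 |
| 105 (three arms) | 3.126 | 1.166 | 87.8% | 88.1% | 0.27 |

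**Number needed for 80% power:** n = ((1.960 + 0.842) / 0.3095)² + 3 = 84.93, so 85. The exact distribution gives 84. From 105, this allows 105 − 85 = 20 subjects without usable PET, or 20/105 = 19.0%.

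**With two indicator terms for arm:** replace n − 3 by n − 5. At n = 105, 0.3095 × √100 − 1.960 = 1.135, giving 87.2%. The number needed rises to 87 (86 exact). The claim still holds at 105, provided that 0.3 is the correlation within arms.

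**What arm adjustment costs if 0.3 is the overall correlation.** Assume, for illustration only, that one arm of three is shifted by 0.5 SD on both measures; the documents give no such shift.

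- Between-arm variance: (1/3)(2/3)(0.5²) = 0.0556.
- Within-arm correlation ρ: (ρ + 0.0556) / 1.0556 = 0.3, so ρ = 0.26.
- Adjusted power at n = 105: atanh(0.261) × 10 − 1.960 = 0.713, giving about 76%.

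**What leaving out the arm term costs under the same kind of assumption.** With true r = 0 within arms and one arm of 35 shifted on both measures, simulation gives a false-positive rate of 5.3% at 0.2 SD, 5.5% at 0.3 SD, 8.3% at 0.5 SD and 24% at 0.8 SD.

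**The case for a change.** The strongest case for a change is that the paragraph does not settle the reading. The sentence that speaks of a total compares it with a group of 35 and with a per-group figure from the literature, and the two power statements before the PET one concern a design with two groups. No two-sided calculation reaches 80% at 35 or 70. Even the pooled reading relies on about 85 usable scans, which the plan does not say. One added sentence would remove the doubt.

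Much of this stands as description. The population is not stated, and the arithmetic at 35 and 70 is right. But the two-group design belongs to the behavioural and fMRI tests, and nothing carries it over to a correlation. The PET sentence refers to the sample without restriction, and the claim is true for that sample. The recruitment figure is also a minimum, so larger arms would only help. To call the claim wrong, one has to put in a test that the plan does not propose.

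The argument for requiring an arm term does not stand as a correction. It depends on an assumed shift in variables that the plan does not name. The inflation is negligible for small shifts. Where the shift is large enough to matter, adjustment has its own price if the 0.3 refers to the overall correlation: about 76% power in place of 88% at 105 in the 0.5 SD example. That is a choice between two defensible analyses.

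**Conclusion.** No change to the plan is needed. The PET power statement is not an arithmetic error: at the planned minimum of 105 subjects, power for a correlation of 0.3 is about 88%, and it stays at or above 80% while about 85 subjects have usable PET data. The figures of 42% and 72% are correct for one and two arms but belong to analyses that the plan does not contain.

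What is left is an unstated PET number and population. An analyst would ordinarily test the correlation once over all subjects with usable PET data, and report that number with a confidence interval; a reader can then see what size of correlation the data could detect.

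The conclusion rests on two assumptions: PET is intended in all three arms, and no more than 20 of 105 subjects lack usable data. The documents give neither a PET subsample nor a loss rate, so neither can be confirmed. If PET was in fact confined to one arm of 35 or two arms totalling 70, the correlation detectable with 80% power would be about 0.46 or 0.33, and the stated 0.3 would be too optimistic. Nothing in the available text indicates such a restriction.
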